3.5.2 Visual Acuity

Visual acuity was assessed at the Month 9, 12, 18, 24, 36, 48, and 60 visits.

4 meter refraction of the sphere, cylinder, and axis of each eye will be measured. Best-corrected ETDRS visual acuity will be measured.

The arithmetic mean of the multiple observations at baseline will be used as the baseline value.

Achievement of visual improvement above the test-retest variation (yes/no) as measured by a number of ETDRS letters will be summarized for study eye and the difference between eyes (study eye minus fellow eye) for all participants.

The 4-meter refraction (sphere, cylinder, and axis) observed values will be summarized for the study eye for all participants.

Summary statistics of all ETDRS visual acuity observed values and the change from baseline by study eye and the difference between eyes (study eye minus fellow eye) for all participants will be presented.

The difference between the study eye and the fellow eye of ETDRS letters, the difference at each visit, along with its change from baseline data, will be summarized. At each post-baseline visit, the change from baseline in the difference between the study eye and the fellow eye will be tested by a nonparametric Wilcoxon signed rank test as the primary method. The p-value from the t-test and the Shapiro-Wilk Normality test will also be provided.

All visual acuity data will be listed.

In-text displays:

- Average Plot of BCVA (ETDRS Letters) Change from Baseline Over Time
- Individual Plot of BCVA (ETDRS Letters) Change from Baseline Over Time

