#### 5.9.3.2 Statistical Methods - Secondary Outcome Analysis

The secondary outcomes are measures of the efficacy of each ATIMP; these will be performed on an individual participant basis and will be primarily descriptive in nature. Standard assessments will be used to measure visual function and established methods of analysis, appropriate for the assessment will be used to evaluate the data. For specialist assessments, data will be analysed by the expert team member(s) who developed the assessment. Final data will be reported descriptively.

Efficacy will be indicated by:

- 1) Any improvement in visual function from baseline that is greater that the test-retest variation for that test and is sustained for at least 2 consecutive assessments.
- 2) Any improvement in retinal function from baseline that is greater than test-retest variation and measurable by electrophysiology (pattern ERG, or full-field ERG).

Measures will be reported individually and aggregated across participants as the proportion who satisfy the above criteria.

Quality of life patient reported outcome measures will be used to correlate a participant's feeling about their own wellbeing with clinical observations.

Any deviations from the original statistical plan will be described in the final report, as appropriate.

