2.3 Study Endpoints

2.3.1 Primary Endpoint

The primary endpoint is to assess the longer-term safety of AAV8-hCARp.hCNGB3 for *CNGB3* gene replacement and AAV8-hG1.7p.coCNGA3 for *CNGA3* gene replacement in the retina administered to participants in the MGT006 and MGT012 studies, measured by the occurrence of any adverse events that are related to the study drug and loss of light perception as measured by a deterioration in visual acuity by 15 or more early treatment diabetic retinopathy study (ETDRS) letters.

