3.5 Efficacy Evaluation

3.5.1 Test-Retest

The test-retest values from studies MGT006 and MGT012 will be used for the MGT007 final analyses.

The protocol describes efficacy as being indicated by:

Any improvement in visual function from baseline that is greater than the test-retest variation for that test and is sustained for at least 2 consecutive assessments.

Participants who have a post baseline reading greater than the test-retest value for at least 2 consecutive assessments will be classed as a visual function improvement for the relevant test.

The test-retest variation for each visual function assessment will be calculated for each participant who has at least one set of test-retest data as:

$$Test - retest = 1.96 \sqrt{S_p^2}$$

where S_p^2 is the within-participant variance for each participant and will be derived as:

$$\frac{(n1-1)\sum_{(yi1-ybar1)}2+(n2-1)\sum_{(yi2-ybar2)}2}{n1+n2-g}$$

Where:

yi1 is the ith baseline observation in the left eye
ybar1 is the mean of baseline observations in the left eye
yi2 is the ith baseline observation in the right eye
ybar2 is the mean of baseline observations in the right eye
n1= number of baseline observations in the left eye
n2= number of baseline observations in the right eye
g is the number of eyes =2

The test-retest variation for each visual function assessment of the difference between the study eye and fellow eye will also be calculated for each participant who has at least one set of test-retest data using the same formula except S_n^2 will be derived as

$$\frac{\sum_{(yi-ybar)}2}{n-g}$$

Where:

yi is the ith baseline observation in the difference of the study eye and fellow eye ybar is the mean of baseline observations in the difference of the study eye and fellow eye n= number of baseline observations in the difference of the study eye and fellow eye (vary from 2 to 3) g is 1

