3.5.3 Contrast Sensitivity

Contrast sensitivity was assessed at the Month 9, 12, 18, 24, 36, 48, and 60 visits.

Contrast sensitivity (LogCS) will be measured using the Pelli-Robson chart. Measurements for each eye and both eyes will be taken.

The arithmetic mean of the multiple observations at baseline will be used as the baseline value.

Achievement of any visual improvement above the test-retest variation (yes/no) as measured by the contrast sensitivity (LogCS) will be summarized for study eye and the difference between eyes (study eye minus fellow eye) for all participants.

Summary statistics of the contrast sensitivity observed values and change from baseline by study eye and assessment by distance at testing for all participants will be presented.

The difference between the study eye and the fellow eye of contrast sensitivity, the difference at each visit, along with its change from baseline data, will be summarized. At each post-baseline visit, the change from baseline in the difference between the study eye and the fellow eye will be tested by a nonparametric Wilcoxon signed rank test as the primary method. The p-value from the t-test and the Shapiro-Wilk Normality test will also be provided.

All contrast sensitivity observed values will be listed.

In-text displays:

- Average Plot of Contrast Sensitivity Change from Baseline Over Time
- Individual Plot of Contrast Sensitivity Change from Baseline Over Time

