3.5.4 Reading Speed

Reading speed was assessed at the Month 9, 12, 18, 24, 36, 48, and 60 visits.

Reading ability, including reading distance (cm), reading acuity (LogMAR), maximum reading speed (words/minute), and critical print size (LogMAR) will be assessed with MNRead and International Reading Speed Texts.

The arithmetic mean of the multiple observations at baseline will be used as the baseline value.

Achievement of visual improvement above the test-retest variation (yes/no) as measured by maximum reading speed will be summarized for study eye and difference between eyes (study eye minus fellow eye) for all participants.

The number and percentage of participants with a reading distance of 40 cm or 25 cm will be presented for the study eye for all participants.

Summary statistics of the maximum reading speed observed values and change from baseline by study eye for all participants will be presented.

The difference between the study eye and the fellow eye of reading speed (words/minute), the difference at each visit along with its change from baseline data will be summarized. At each post-baseline visit, the change from baseline in the difference between the study eye and the fellow eye will be tested by nonparametric Wilcoxon signed rank test as the primary method. The p-value from the t-test and the Shapiro-Wilk Normality test will also be provided.

All reading speed data will be listed.

In-text displays:

- Average Plot of Maximum Reading Speed Change from Baseline Over Time
- Individual Plot of Maximum Reading Speed Change from Baseline Over Time

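### The SAP counts sustained improvement beyond test-retest variation but not sustained deterioration beyond the same limit, so the responder proportion has no chance benchmark

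*SAP*

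**What the plan says.** SAP 3.5.1 sets one class. A participant who exceeds the test-retest value at two or more consecutive assessments "will be classed as a visual function improvement for the relevant test". The limit is "Test - retest = 1.96" times the square root of a variance that "is the within-participant variance for each participant", taken from that participant's own baseline readings.

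Three sections tabulate this class:
- Acuity (SAP 3.5.2): "Achievement of visual improvement above the test-retest variation (yes/no) as measured by a number of ETDRS letters will be summarized".
- Contrast sensitivity (SAP 3.5.3): "Achievement of any visual improvement above the test-retest variation (yes/no) as measured by the contrast sensitivity (LogCS) will be summarized".
- Reading speed (SAP 3.5.4): "Achievement of visual improvement above the test-retest variation (yes/no) as measured by maximum reading speed will be summarized".

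Each is given for the study eye and for study eye minus fellow eye. Protocol 5.9.3.2 likewise defines efficacy by improvement only, and has the results "aggregated across participants as the proportion who satisfy the above criteria".

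The only deterioration threshold is in SAP 2.3.1, "a deterioration in visual acuity by 15 or more early treatment diabetic retinopathy study (ETDRS) letters". It covers acuity alone and has no two-assessment requirement. SAP 3.4 (Safety Evaluation) specifies no acuity table, although the primary objective (Protocol 4.5.1, SAP 2.1.1) includes assessment of visual acuity.

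**The concern.** Two uses of the data are affected.

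**Efficacy.** Random error alone pushes some participants past the limit twice in a row, and under symmetric error it pushes as many the other way. The study has no comparator (Protocol 4.4). The number who worsen by the same rule is therefore the most direct indication of how many improvers chance would produce. The plan reports one tail and not the other.

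**Safety.** A participant with a sustained acuity loss beyond measurement error, but under 15 letters, is shown in the improvement table only as not improved. The same holds for any sustained loss in contrast sensitivity or reading speed, where there is no deterioration threshold at all.

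**Working it through.** The documents state no false-classification rate, so there is no figure of the plan's own to reproduce. The rule was simulated instead.

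**Inputs from the SAP**
- Limit: 1.96 × S, with S from the participant's own baseline readings (3.5.1).
- Baseline value: the mean of the baseline readings (3.5.2 to 3.5.4).
- Visits: Months 9, 12, 18, 24, 36, 48 and 60, so seven.
- Baseline readings: 2 to 3, stated for the between-eye difference in 3.5.1.
- Participants dosed: 23 + 11 = 34 (2.2.3).

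**Assumptions**
- The per-eye number of baseline readings is also 2 to 3.
- The SAP's post-baseline reading is taken as a change from baseline.
- There is no true change. Errors are independent and normal, with equal variance in both eyes and at all visits.
- No visit is missing, and all 34 are followed.

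**Formulas.** Let SS1 and SS2 be the sums of squares about each eye's baseline mean, with n readings per eye.
- Study eye, ordinary pooling: S² = (SS1 + SS2)/(2n − 2).
- Study eye, as printed: S² = [(n − 1)SS1 + (n − 1)SS2]/(2n − 2). This equals ordinary pooling at n = 2 and is twice it at n = 3.
- Between-eye difference: S² = SS/(n − 1).
- Improved: change > 1.96 S at two consecutive visits. Deteriorated (not in the plan): change < −1.96 S at two consecutive visits.

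**Results** (400,000 simulated participants per row)

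| Comparison | Baseline readings | Improved | Deteriorated | Expected improved of 34 |
|---|---|---|---|---|
| Study eye | 2 | 13.9% | 13.8% | 0.139 × 34 = 4.7 |
| Study eye, ordinary pooling | 3 | 7.6% | 7.6% | 0.076 × 34 = 2.6 |
| Study eye, as printed | 3 | 3.0% | 3.0% | 0.030 × 34 = 1.0 |
| Between-eye difference | 2 | 21.3% | 21.2% | 0.213 × 34 = 7.2 |
| Between-eye difference | 3 | 12.4% | 12.4% | 0.124 × 34 = 4.2 |

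With five visits instead of seven, the improved rates in the same order are 10.9%, 5.6%, 2.2%, 17.1% and 9.6%.

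**What the missing row would detect.** Suppose a true study-eye loss of 2 within-participant SDs at every visit. The mirrored rule would flag about 69% of participants with 2 readings, or with 3 readings and ordinary pooling. It would flag 43% with 3 readings and the printed formula. The planned improvement row would flag 0.2% or fewer.

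**Acuity losses without a category.** The documents give no within-participant SD. For assumed values of S of 2, 3, 4, 5 and 7 letters, the limit 1.96 S is 3.9, 5.9, 7.8, 9.8 and 13.7 letters. A sustained gain between that limit and 15 letters is counted; a loss of the same size is not. The gap closes at S = 15/1.96 = 7.65 letters.

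**The case against.** A reader might infer that moderate losses disappear from the report, or that deterioration is counted nowhere. The documents do not support that.
- SAP 3.5.2 to 3.5.4 plan change-from-baseline summaries, individual plots and full listings. SAP 3.1.4 adds Q1 and minimum to the summaries. With 34 participants, individual plots show a good deal.
- An acuity loss of 15 or more letters is part of the primary endpoint.
- Protocol 5.10.4.5 has clinically significant abnormal test results recorded as adverse events, and these enter the counts in SAP 3.4.1.

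A reader might also infer that gains and losses can never offset each other. That is true only of the responder table: mean changes and the signed-rank tests use signed values, and the between-eye difference gives an internal comparison.

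Nor does the SAP depart from the protocol here. The protocol itself defines these outcomes as improvement, descriptively, with no responder-rate test or success threshold.

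All of this stands, but it does not replace the count. The summaries and tests work visit by visit and do not apply the two-assessment rule to a person. The plots and listings leave the reader to derive the number. Adverse event recording depends on a judgement of clinical significance.

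Two further cautions also stand. A deterioration row does not lower the chance rate of improvement, which comes from the limit and the number of visits; it only makes that rate visible. And it is a fair benchmark only if errors are roughly symmetric. Learning effects or floor effects would make it approximate, and with a handful of participants in each direction the two counts should be shown side by side rather than subtracted.

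**Conclusion.** The point holds in a limited form. There is no categorical count of sustained deterioration beyond test-retest for any of the three analysed visual function tests, and none of acuity losses under 15 letters except those recorded as adverse events. Participants who worsen are grouped with those who do not change, and an uncontrolled responder proportion is left without a chance benchmark.

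The chance rate is too large to ignore: about 14% (2 readings) or 3% to 8% (3 readings) in the study eye, and about 21% or 12% for the between-eye difference. These figures rest on the stated assumptions; correlated errors, unequal variances, learning effects or missing visits would change them. The uncounted band of acuity loss exists for any participant whose computed S is below 7.65 letters. This is an inexpensive improvement to reporting, not a flaw that hides the data.

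**What to change.** - **SAP 3.5.1:** define sustained deterioration as a change from baseline below minus the test-retest value at two or more consecutive assessments.
- **SAP 3.5.2 to 3.5.4:** replace the yes/no row with improved / unchanged / deteriorated, for the study eye and for the between-eye difference. State how a participant who meets both rules at different times is shown.
- **SAP 3.4:** add the acuity deterioration row, and specify a table for the 15-letter loss named in 2.3.1.

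No new data are needed. The cost is one sign-reversed flag and one extra row per table, plus the table for the 15-letter loss, and SAP section 1 leaves room for this because the plan is to be finalised before database lock. The sponsor should accept that the reported picture may look less favourable.

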#### 4.4 Explanation for Choice of Comparators

This is a follow-up study to gene therapy studies MGT006 and MGT012, and is non-interventional. There is no comparator used in this study.

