#### 5.4.1.1.2 Functional and Participant-Related Outcome assessments

Where possible the participant will complete an age appropriate Impact of Visual Impairment (IVI) vision-specific quality of life questionnaire, and EQ5D-5L questionnaire.

Reading ability including reading acuity, maximum reading rate, and critical print size will be assessed with MNRead and International Reading Speed Texts.

The degree of light sensitivity (photoaversion) will be investigated in 2 ways (i) Objectively by measurement of palpebral aperture narrowing in response to gradually increasing light intensity and (ii) Subjectively by participant reported symptomatology.

Best-corrected ETDRS visual acuity will be measured in each eye. Contrast sensitivity will be measured using the Pelli-Robson chart or computerised (achromatic) spatial contrast sensitivity function tests.

Colour vision will be assessed comprehensively using plate tests and computerised tests probing colour discrimination along all 3 axes of colour and other testing methods may also be used as appropriate.

Retinal sensitivity will be determined using static perimetry and full field stimulus testing (FST) where available.

Full-field electroretinography (ERG), pattern ERG (PERG) will be performed according to the International Society for Clinical Electrophysiology of Vision (ISCEV) standards to assess both generalised retinal (rod and cone systems) and isolated macular function. Modified ISCEV protocols may be necessary in young children using internationally recognised modified protocols. ERG assessments may be performed under general anaesthesia if considered appropriate. ERG data will be analysed and interpreted by dedicated full-time Clinical Visual Electrophysiology Consultants at Moorfields Eye Hospital, UK, with extensive experience and who are directly involved in determining ISCEV standards.

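### The SAP summarises efficacy for the study eye and the between-eye difference but never for the fellow eye, so a sustained fellow-eye loss can be labelled visual improvement

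*SAP*

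**What the plan says.** Protocol section 5.4.1.1.2 has acuity taken for both eyes: "Best-corrected ETDRS visual acuity will be measured in each eye". SAP 3.5.3 likewise has contrast sensitivity measured for each eye, and every between-eye difference needs a fellow-eye value. The data therefore exist.

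What the SAP summarises is narrower:

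- **Visual acuity (SAP 3.5.2).** The yes/no improvement result "will be summarized for study eye and the difference between eyes (study eye minus fellow eye) for all participants". Observed values are handled in the same way, and "the change from baseline by study eye and the difference between eyes (study eye minus fellow eye) for all participants will be presented".
- **Contrast sensitivity (SAP 3.5.3).** The yes/no result again covers the study eye and the difference. For the measurements, the plan is "Summary statistics of the contrast sensitivity observed values and change from baseline by study eye and assessment by distance at testing", with the difference summarised separately.
- **Reading speed (SAP 3.5.4).** Improvement "as measured by maximum reading speed will be summarized for study eye and difference between eyes (study eye minus fellow eye"). Values and change are summarised for the study eye, and the difference separately.

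For all three tests, the change in the difference is tested at each post-baseline visit with a Wilcoxon signed rank test. Individual values go to listings; for acuity, "All visual acuity data will be listed". The planned average and individual plots do not say which eye they show.

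SAP 3.5.1 classes a participant as improved on a test when the result exceeds the test-retest value at two or more consecutive assessments. The difference has its own threshold, computed from the baseline differences. Nothing in the rule for the difference refers to the study eye's own result.

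Protocol 4.4 states: "There is no comparator used in this study". SAP section 4, which lists changes from the protocol analysis, does not mention the fellow eye.

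**The concern.** The secondary objective is to explore whether visual function improves. A rise in study eye minus fellow eye can come from a better study eye or a worse fellow eye, and the yes/no rule gives both the same label. The planned tables show the study-eye proportion and the difference proportion as separate margins. They do not show which difference responders had no study-eye response.

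There is a second, smaller gap. The study-eye proportion is the protocol's own efficacy measure (Protocol 5.9.3.2), in an open-label study that includes children and repeats the tests at seven visits. No fellow-eye proportion under the same rule stands beside it. With 23 and 11 participants dosed (SAP 2.2.3), a few participants whose label rests on the fellow eye visibly change a reported proportion.

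**Working it through.** The documents give no responder rate or power figure on this point, so there is nothing to reproduce. The check is algebra followed by an illustration.

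**1. Algebra.** Let ΔS and ΔF be the changes from baseline in the study and fellow eyes. The change in the difference is

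ΔD = ΔS − ΔF.

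A study eye at 0 and a fellow eye at −10 letters give ΔD = 0 − (−10) = +10. The participant is a difference responder if ΔD > 1.96·S_D at two consecutive visits, with S_D² = Σ(d_i − d̄)²/(n − 1) from the n baseline differences (SAP 3.5.1 with g = 1). ΔS does not enter separately.

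**2. Inputs for the illustration.**

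- From the SAP: threshold 1.96·S; two or more consecutive assessments; seven visits (Months 9, 12, 18, 24, 36, 48 and 60); baseline value taken as the mean of the replicates; two to three baseline readings (stated for the difference).
- Assumed, not in the documents: normal independent errors, within-eye SD 3 letters, three readings, complete visits, a constant shift in every participant, and the rule read as change from baseline. The study-eye threshold uses the conventional pooled variance, (SS1 + SS2)/(n1 + n2 − 2).

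**3. Results** (200,000 simulated participants per row):

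| Study-eye shift | Fellow-eye shift | Study-eye responders | Fellow-eye responders | Difference responders | Difference but not study-eye responders |
|---|---|---|---|---|---|
| 0 | 0 | 8% | 8% | 12% | 9% |
| 0 | −1 | 8% | 4% | 17% | 13% |
| 0 | −5 | 8% | under 1% | 45% | 38% |
| +5 | +5 | 57% | 57% | 12% | 1% |

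For the dosed numbers, 12% and 45% are about 3 and 10 of 23, or about 1 and 5 of 11.

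**4. Sensitivity of the 45%.** It is 64% at SD 2 and 36% at SD 4. With two baseline readings it is 53%, where the no-change rate is itself 21%. With a between-eye error correlation of 0.5 it is 61%. The pooled variance as printed in SAP 3.5.1 multiplies each eye's sum of squares by n − 1. Using it with three readings leaves the difference rates unchanged, because the difference has its own formula. It lowers the 8% study-eye rate to 3% and the shared-gain 57% to 33% in both eyes.

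**5. What the planned tables can recover.** Mean fellow-eye change equals mean ΔS minus mean ΔD if the same participants contribute. The fellow-eye responder rate cannot be obtained from the summaries. The two margins only bound the proportion with a difference response and no study-eye response. With 8% and 45% the bounds are 45 − 8 = 37% to 45%, which is tight. With a study-eye rate of, say, 40% and the same 45%, they are 45 − 40 = 5% to 45%, which says little.

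**The case against.** The strongest reply is that the two planned summaries check each other. A gain shared by both eyes, such as practice, raises the study-eye rate to 57% but leaves the difference rate at its no-change 12%. A fellow-eye loss raises the difference rate to 45% but leaves the study-eye rate near 8%. A reader who looks at both would notice either pattern. This stands. A reader might infer that practice or maturation would go undetected; the documents do not support that, because the difference analysis is there to remove shared effects.

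Other stronger readings also fail:

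- **That fellow-eye results go unreported.** Individual values are listed, the outcomes are descriptive and assessed participant by participant, at most 34 people were dosed, and the mean change can be back-calculated.
- **That any fellow-eye worsening counts as improvement.** The change in the difference must pass its own threshold at two consecutive visits, and a similar study-eye fall cancels it. Even with a 5-letter loss, 55% are not so classed.
- **That a 5-letter loss is to be expected.** Protocol 4.1 and 4.2 describe the condition as largely non-progressive, and neither document suggests systematic fellow-eye decline.
- **That the SAP contradicts Protocol 4.4.** A within-person contrast is not a comparator arm, so leaving it out of section 4 is a minor matter.
- **That the fellow eye is an untreated control.** The wording suggests it, but neither document says so, and the parent protocols are not among them.

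Requiring the study eye also to respond before counting a difference response would create a new composite endpoint, which is debatable and not needed here.

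What the reply does not answer is attribution. Two margins do not show whose difference response came without a study-eye response, and reconstructing this from listings is work that the tables should do.

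**Conclusion.** The point holds as a gap in presentation and labelling of the secondary efficacy results, and it is worth closing. It is not an error that invalidates them. SAP 3.5.2 to 3.5.4 plan no fellow-eye summary and no same-rule fellow-eye rate, and the rule in 3.5.1 lets a sufficiently large and sustained fellow-eye loss be called visual improvement. That follows from the algebra and needs no assumption.

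The size does depend on assumptions. With an unchanged study eye and the inputs above, difference responders go from 12% with a stable fellow eye to 17% at a 1-letter loss and 45% at a 5-letter loss. The 1-letter figure shows that the effect is small if the fellow eye barely changes. The 5-letter figure shows what happens if it does change, not what the documents predict. For shared gains, the only thing missing is a fellow-eye rate to set beside the study-eye rate.

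**What to change.** Before database lock, when SAP section 1 says the SAP will be final:

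1. In SAP 3.5.2 to 3.5.4, add fellow-eye observed values, change from baseline and responder rate under the same rule, beside the study eye.
2. Cross-tabulate difference responders by study-eye and fellow-eye responder status for each test. Describe a difference response without a study-eye response as a between-eye change, not as visual improvement.
3. State which eye each average and individual plot shows.
4. Note in section 4 that the fellow eye serves as a within-participant reference, after confirming from the parent studies that it was not treated.

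The cost is a few table columns and one cross-tabulation per test, all from data already collected. The proportion described as improved on the between-eye measure may fall.

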2.2.3 Sample Size Determination

This is a long-term follow-up study; therefore, there is no formal sample size calculation.

23 and 11 participants were randomized and dosed in the MGT006 and MGT012 studies, respectively. All participants enrolled in the MGT006 and MGT012 studies were invited to participate in this follow-up study.

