3.1.4 Summary Statistics

Categorical data will generally be summarized with counts and percentages of subjects. The denominator used for the percentage calculation will be clearly defined. Continuous data will generally be summarized with descriptive statistics including n (number of non-missing values), mean, median, standard deviation, Q1, Q3, minimum, and maximum.

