5 PROGRAMMING SPECIFICATIONS

Analyses will be performed using SAS® version 9.3 or higher. All available data will be presented in subject data listings which will be sorted by subject and visit date as applicable. Detailed Programming Specifications will be provided in a separate document.

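### SAP 3.5.2 plans to summarise cylinder axis without a valid method, and the default statistics in 3.1.4 do not suit an angle that repeats every 180 degrees

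*SAP*

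**What the plan says.** Refraction is recorded in SAP 3.5.2 as three components per eye: "4 meter refraction of the sphere, cylinder, and axis of each eye will be measured". The summary instruction in the same section is: "The 4-meter refraction (sphere, cylinder, and axis) observed values will be summarized for the study eye for all participants". Axis is thus named as something to be summarised, next to sphere and cylinder.

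SAP 3.1.4 supplies two defaults. For numeric data: "Continuous data will generally be summarized with descriptive statistics including n (number of non-missing values), mean, median, standard deviation, Q1, Q3, minimum, and maximum". For categories: "Categorical data will generally be summarized with counts and percentages of subjects". No axis categories are defined anywhere, so an axis in degrees falls under the numeric default.

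SAP 3.5.2 also sets a baseline rule: "The arithmetic mean of the multiple observations at baseline will be used as the baseline value". The rule is not restricted to ETDRS letters, so it could be read as covering axis.

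Neither section mentions circular statistics, a power-vector conversion, a listing-only rule for axis, or what to do with an eye that has no cylinder. SAP 3.1.5 adds that data are presented by dose level. Its table shows groups of 3, 12, 3 and 5 for MGT006 and 3, 3 and 5 for MGT012.

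**The concern.** An axis of 1 degree and an axis of 179 degrees are 2 degrees apart, but ordinary arithmetic treats them as 178 apart and puts their mean at 90, perpendicular to both. The SD and quartiles rest on the same false ordering, and the median can fail in the same way. Axis also has no meaning without its cylinder power: an eye with zero cylinder has no axis, and an eye with very little cylinder should count for little.

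A programmer who follows the SAP literally would put such figures into the refraction table of the study report. A reader could take them as the typical orientation of astigmatism in the treated eyes, or see a shift between visits that is only a wrap-around effect. The treatment was given by subretinal surgery, and refraction is part of the context for reading best-corrected acuity over 60 months, so the table should not mislead.

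**Working it through.** The documents contain no refraction data and state no figure on this point, so there is nothing to reproduce. All axis and cylinder values below are assumptions chosen to show how the statistics behave. Group sizes come from SAP 3.1.5 and from SAP 2.2.3: "23 and 11 participants were randomized and dosed in the MGT006 and MGT012 studies, respectively", which is 23 + 11 = 34 in total.

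**Formulas.** For cylinder C (dioptres, minus-cylinder form) and axis a:

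- J0 = −(C/2)·cos(2a) and J45 = −(C/2)·sin(2a)
- average J0 and J45 over eyes, then convert back: cylinder = −2·√(J0² + J45²), axis = ½·atan2(J45, J0), modulo 180
- with equal cylinders this is the doubled-angle circular mean

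**Three eyes at 5, 175 and 178** (equal cylinders; the size of a real dose group).

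- Arithmetic mean: (5 + 175 + 178)/3 = 358/3 = 119.3.
- Doubled angles are 10, 350 and 356. Cosines sum to 0.985 + 0.985 + 0.998 = 2.967; sines sum to 0.174 − 0.174 − 0.070 = −0.070. Half of atan2(−0.070, 2.967) is −0.7, that is 179.3.
- Difference: 60 degrees. The median here is 175, so it happens to be close.

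**Two-eye examples.**

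| Eyes (cylinder at axis) | Arithmetic mean and median | SD | Power-vector mean |
|---|---|---|---|
| −2.00 at 5; −2.00 at 175 | 90 | 120.2 | −1.97 at 180 |
| −2.00 at 85; −2.00 at 95 | 90 | 7.1 | −1.97 at 90 |
| −3.00 at 10; −0.25 at 100 | 55 | 63.6 | −1.38 at 10 |
| −2.00 at 10; zero cylinder entered as 90 | 50 | 56.6 | −1.00 at 10 |

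The first row is off by 90 degrees, the largest error possible because two axes can never differ by more than 90. The first and second rows have the same mean and median although the orientations are perpendicular. The last two rows show the effect of ignoring cylinder power.

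**Effect of group size.** When one eye drifts across the 0/180 boundary, the arithmetic mean jumps by about 180/n degrees: 180/3 = 60, 180/5 = 36, 180/12 = 15, 180/34 = 5.3. The jump from a single eye shrinks with n, but the bias does not, as the simulation shows.

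**Simulation** (5,000 runs per row; cylinder −2.00 D in every eye; axis normally distributed with SD 15 degrees around the stated centre).

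| n | Centre | Arithmetic mean: average (2.5th to 97.5th percentile) | Median: 2.5th to 97.5th percentile | Average SD | Vector-mean axis: 2.5th to 97.5th percentile |
|---|---|---|---|---|---|
| 34 | 180 | 90.1 (64.2 to 116.5) | 15.0 to 165.1 | 78.6 | −5.1 to 4.9 |
| 23 | 180 | 90.2 (58.7 to 122.1) | 13.1 to 167.1 | 78.5 | −6.0 to 6.2 |
| 11 | 180 | 89.6 (41.1 to 138.3) | 9.1 to 170.6 | 78.2 | −9.0 to 9.2 |
| 34 | 90 | 90.0 (84.8 to 95.1) | 83.6 to 96.1 | 14.9 | 84.8 to 95.0 |

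With axes centred on 180, the arithmetic mean settles near the perpendicular orientation and the SD is about five times the true spread (78.6/15 = 5.2). With axes centred on 90, the default statistics are acceptable.

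**The case against.** The strongest reply is that SAP 3.5.2 never says axis will be averaged. It says the values will be summarised, SAP 3.1.4 qualifies its rule with the word generally, and SAP 5 states: "Detailed Programming Specifications will be provided in a separate document". That document is not available here and may handle axis properly. This stands to the extent that averaging is inferred from the default rather than stated. It does not remove the point, because the SAP tells the programmer to summarise axis and offers only an unsuitable method.

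A reader might also infer four stronger things, which the documents do not support:

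- *The whole refraction table is wrong.* Sphere and cylinder power are not circular. Under one sign convention their means and ranges are valid. Mean cylinder describes the amount of astigmatism and leaves out its orientation.
- *The axis averages are bound to be meaningless.* The error depends on where axes cluster. Near 90 degrees the default works, and no refraction data are given.
- *A refractive shift in a treated eye could not be seen.* SAP 3.5.2 lists all visual acuity data, and SAP 5 lists all available data by subject and visit. With 34 dosed participants, a shift can be followed eye by eye.
- *Acuity results are affected.* Refraction is not an endpoint in SAP 2.3. The tests and responder rule in SAP 3.5.2 use ETDRS letters, which are measured with best correction and do not depend on how axis is tabulated.

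**Conclusion.** The point holds as a minor one. Following the SAP as written leads to statistics that are not valid for axis. They can be up to 90 degrees off when axes lie near 0/180, and they are least stable in the dose groups of 3 to 5. The damage is limited to the axis rows of one descriptive table and, if the baseline rule is applied to refraction, to averaged baseline axes.

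This rests on two assumptions: that axis is recorded in degrees and handled by the SAP 3.1.4 numeric default, and that at least some participants' axes lie near 0/180 or in mixed orientations. The examples show what the method can do; they do not measure an error in this study's data.

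**What to change.** Amend SAP 3.5.2 before database lock:

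- Take axis out of the summary table and state that it is never arithmetically averaged, including when repeat baseline observations are combined.
- List sphere, cylinder and axis together for each eye and visit.
- In place of axis, summarise spherical equivalent (sphere + cylinder/2), J0 and J45 for the study eye. Sphere and cylinder magnitude may stay. An eye with zero cylinder then needs no special rule, since J0 = J45 = 0.
- Change from baseline in these three quantities is optional. The SAP does not now plan it for refraction. Because SAP 3.1.1 takes baselines from the parent-study analyses, it may require deriving the vector components from the parent studies' refractions.

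The cost is three derived variables from data already collected, one changed table shell and a consistent cylinder-sign convention. J0 and J45 are less familiar to clinical readers, so a footnote explaining them would help. A minimal alternative is to list axis and leave it out of the summary altogether. That removes the invalid figures but gives no group-level description of orientation.
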